6.3.3. Analyses of secondary endpoints

- Proportion (95% CI) seroconverting to a positive response to SARS-CoV-2 IgG serology after two doses of vaccine, at 3 months and 6 months after the second vaccine dose, measured in the "two-dose vaccine population" compared with the control group.
- Proportion (95% CI) experiencing adverse events, with AE/SAE/SUSAR. Number and proportion (95% CI) experiencing local reactions and systemic reactions are measured in the "Full analysis set population".
- Proportion (95% CI) receiving a new diagnosis of SARS-CoV-2 infection through a positive PCR test is measured in the "Full analysis set population."

- Comparisons are made with the control group.

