- A diary is given to the study participant/information about the eDiary.

5.2.3. 10-day follow-up (10-day FU) after the first vaccine dose (+/-3 days)

Sampling group A

All contact between study participants and study staff (research nurse or investigator) can be done remotely by phone or chat, if the Always Open function is available. Can also be done on site, if it coincides with the study participant's regular visit to the study unit or if the study participant prefers to be sampled at the study unit.

Blood samples can be taken at any of the Karolinska University Laboratory's sampling units in Stockholm, and saliva samples can be sent in a stamped envelope to the Karolinska Institute.

- Review of the diary (local and systemic reactogenicity).
- Review of adverse events (AE/SAE/SUSAR).
- Review of concomitant medication (all new drugs, including immunosuppressive/immunoglobulin treatments).
- Testing for SARS-CoV-2 serology and more detailed analyses of humoral immunity (blood).
- Sampling for humoral immunity (saliva).

Sampling group B

All procedures are performed at the study unit, as sampling for peripheral blood mononuclear cell (PBMC) samples is required for cellular immunity at the study unit:

- Review of the diary (local and systemic reactogenicity).
- Review of adverse events (AE/SAE/SUSAR).
- Review of concomitant medication (all new drugs, including immunosuppressive/immunoglobulin treatments).
- Sampling for SARS-CoV-2 serology and more detailed analyses of humoral immunity (blood).
- Sampling for humoral immunity (saliva).
- Sampling for analysis of cellular immunity (blood).

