5.3.3. Features via the "Always Open" app and consent application

1.1.1. Always open

In collaboration with the Stockholm County Council (SLSO), we plan to build process support for this study within "Always open", an application (app) developed by the Stockholm County Council (SLSO) that offers various healthcare contacts such as video meetings, chat with healthcare personnel, etc. All logins to the app are done with mobile Bank ID. The app is used routinely in routine healthcare, especially in outpatient care. All health information that appears via the app will be recorded in the patient's medical records, which constitute source data.

We plan to use this app to:

- Have video visits with research subjects during screening and, if necessary, during the study period.
- As a complement, use the app to send pictures of the injection site when necessary. Any pictures will be printed and scanned into the patient's medical record.
- Record local and systemic reactogenicity using eDagbok, where study participants self-record their reactions daily for 7 days after the vaccine dose. Information from Alltid öppet will be recorded in the patient's medical records, which constitute source data. A paper version of the diary can be filled in if eDagbok cannot be used.
- Chat with study participants at the predefined contact times. Chat content will be recorded in the patient's medical records, in the same way as if communication had taken place via a telephone call. Test results from SARS-CoV-2 serology can be communicated via chat at the end of the study.
- Give study participants the opportunity to ask questions to study staff during the study period.

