5.5.3. Reactogenicity (Diary)

Each study participant will be provided with a diary. Study participants will record and rate the severity of symptoms in a diary according to 5.8.3. The evaluation will take place from the day of vaccination until 7 days after the dose, after each vaccine dose.

A reactogenicity event recorded in the diary will not be recorded as an AE unless it meets the criteria for an SAE.

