5.8.3. Assessment of local and systemic reactogenicity

1.1.1.3 Assessment of local reaction at the injection site

The occurrence of pain, redness, and swelling at the injection site is reported in a diary completed by the patient for the period from the vaccine dose to 7 days after the dose for both the first and second vaccine doses. Local bleeding is observed by staff after injection during the observation period. For individuals who have difficulty filling in a diary, study staff will contact the patient on days 2 and 7 after the vaccine dose to collect data by telephone.

The rationale for the 7-day period after the vaccine dose is that local reactions have been studied in 8,183 study participants within 7 days after injection, and these reactions usually began within two days after vaccination and disappeared after 1-2 days. Only 1% reported severe pain, and a lower frequency was reported for redness or swelling. These reactions were less common in people over 55 than in younger people. We do not expect a higher frequency or more severe degree of these local reactions, possibly the opposite in immunosuppressed individuals. An exception may be local bleeding at the injection site, due to existing medical conditions with coagulopathy or anticoagulant treatments.

Table 1. Local Reaction Grading Scale

	Mild (Grade 1)	Moderate (Grade 2)	Severe (Grade 3)	Potentially Life Threatening (Grade 4)
Pain at the injection site	Does not interfere with activity	Interferes with activity	Prevents daily activity	Emergency room visit or hospitalization for severe pain
Redness	>2.0 cm to 5.0 cm (5 to 10 measuring device units)	>5.0 cm to 10.0 cm (11 to 20 measuring device units)	>10 cm (≥ 21 measuring device units)	Necrosis or exfoliative dermatitis
Swelling	>2.0 cm to 5.0 cm (5 to 10 measuring device units)	>5.0 cm to 10.0 cm (11 to 20 measuring device units)	>10 cm (≥ 21 measuring device units)	Necrosis

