6.2. Analysis populations

Population	Description of population
Full analysis set population	All study participants who have received at least one dose of vaccine
Population with two doses of vaccine	All study participants who received two doses of vaccine and had a test result at 2 weeks after the second vaccine dose.
Population with evaluable reactogenicity after dose 1	All study participants who have received at least one dose of vaccine and have at least one measurement of reactogenicity after the first dose.
Population with Evaluable reactogenicity after dose 2	All study participants who have received two doses of vaccine, and had at least one measurement of reactogenicity after the second dose.

The number and percentage of study participants who are enrolled in the study, complete the study, and discontinue the study will be presented. Reasons for discontinuation will also be presented.

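### Section 6.3.3 measures diary reactions in everyone dosed, while the two evaluable-reactogenicity populations defined in 6.2 are used by no analysis: a minor fix to a secondary endpoint

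*Combined protocol and SAP*

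**What the plan says.** Section 6.3.3 assigns the population for the reactogenicity endpoint: "Number and proportion (95% CI) experiencing local reactions and systemic reactions are measured in the" full analysis set. Comparisons are made with the control group, and section 6.4 names the chi-square test. Section 6.2 defines the full analysis set as all participants who received at least one dose; no diary entry is required.

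The same table in 6.2 defines two populations made for this endpoint. The first, for dose 1, reads: "All study participants who have received at least one dose of vaccine and have at least one measurement of reactogenicity after the first dose". The second, for dose 2, reads: "All study participants who have received two doses of vaccine, and had at least one measurement of reactogenicity after the second dose". Neither is named in 6.3.1 to 6.3.4 or in 6.4.

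The diary runs from the day of vaccination to day 7 after each dose (5.5.3). Neither the endpoint in 4.2 nor the analysis in 6.3.3 says whether the proportion is after dose 1, after dose 2 or after either. No section says how a participant without diary data is counted.

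The adverse event data cannot fill the gap, because 5.5.3 states: "A reactogenicity event recorded in the diary will not be recorded as an AE unless it meets the criteria for an SAE".

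**The concern.** The plan names a denominator that includes people for whom the outcome may be unknown, and leaves unused the two populations that it built to exclude them. If the full analysis set is applied as written, a person with no diary data stays in the denominator and cannot enter the numerator, which scores that person as a non-reactor.

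Within one group this lowers the reported proportion. Between groups it matters only if diary return differs. Fewer diaries from patients would produce an apparent deficit of reactions in patients, the same direction as the milder reactogenicity that section 2.2 expects, so an artefact could pass for confirmation. Fewer diaries from controls would produce the opposite error. Because no dose is stated either, two analysts could report different proportions from the same diaries.

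**Working it through.** **No planned figure to reproduce.** The documents give no expected reaction rate for this population, no diary-return rate and no power for this endpoint. The rates below are assumptions, chosen to show a range.

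**Inputs.** From section 5.1.1: 90 per patient group and 90 controls. From section 6.4: chi-square test of each patient group against controls. Assumed: the same true per-dose rate p in both groups; share of diaries missing m; a missing diary scored as no reaction. Base case p = 70%, m = 5% in controls and 10%, 15% or 20% in patients. The last column of each table is the exact probability that the Pearson chi-square test (no continuity correction, two-sided 0.05) declares a difference, summed over both binomial distributions.

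**Per-dose proportion.** Reported rate = p(1 − m). Controls: 0.70 × 0.95 = 66.5%.

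| Patients missing | Patients reported | Spurious deficit | Declared significant |
|---|---|---|---|
| 10% | 0.70 × 0.90 = 63.0% | 3.5 points | 8% |
| 15% | 0.70 × 0.85 = 59.5% | 7.0 points | 17% |
| 20% | 0.70 × 0.80 = 56.0% | 10.5 points | 31% |

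At a 1% level (Bonferroni for five patient groups) the last column becomes 2%, 6% and 13%.

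**Any-dose proportion, same people react after both doses, diaries lost independently.** A reactor is missed only if both diaries are lost, so the reported rate = p(1 − m²). Controls: 0.70 × (1 − 0.0025) = 69.8%.

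| Patients missing | Patients reported | Spurious deficit | Declared significant |
|---|---|---|---|
| 10% | 69.3% | 0.5 points | 5% |
| 15% | 68.4% | 1.4 points | 5% |
| 20% | 67.2% | 2.6 points | 7% |

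**Any-dose proportion, reactions and losses both independent between doses.** Reported rate = 1 − (1 − p(1 − m))². Controls 88.8%; patients 86.3%, 83.6% and 80.6%; deficits 2.5, 5.2 and 8.1 points; declared significant in 8%, 17% and 33%. If the same people react after both doses and the same people return neither diary, the per-dose figures apply.

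**Low missingness.** Per dose, 2% missing in controls and 5% in patients: 0.70 × 0.98 = 68.6% against 0.70 × 0.95 = 66.5%, a deficit of 2.1 points, declared significant in 6%.

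**Other true rates, per dose, 5% against 10–20% missing.** p = 50%: 0.50 × (0.05 to 0.15) = 2.5 to 7.5 points. p = 80%: 0.80 × (0.05 to 0.15) = 4 to 12 points.

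**Direction.** With 20% missing in controls and 5% in patients, the 10.5-point error has the opposite sign.

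**Evaluable populations instead.** With 10%, 15% and 20% missing, about 81, 76 or 72 patients remain (90 × 0.90, 0.85, 0.80) against about 86 controls (90 × 0.95). Both groups report 70% and the test rejects in 5.0%, 4.9% and 4.8%. This holds only if diary return is unrelated to reacting and the returned diaries are complete.

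**The case against.** The strongest reply is that the harm is assumed. Nothing in section 6 says that a missing diary is scored as no reaction. If analysts drop missing diaries, the error disappears, and the names and per-dose definitions of the evaluable populations suggest that a by-dose analysis was intended and a cross-reference was lost. That reading is plausible, but dropping missing diaries is the evaluable analysis under another name, and 6.3.3 names a different set.

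The second reply is that missingness should be small and similar across groups. This largely stands. Staff carry out a "Review of the diary (local and systemic reactogenicity") in both sampling groups at the 10-day contact (5.2.3) and the 2-week contact (5.2.5). Section 5.3.3 adds: "A paper version of the diary can be filled in if eDagbok cannot be used". Section 5.8.3 adds: "For individuals who have difficulty filling in a diary, study staff will contact the patient on days 2 and 7". These safeguards apply alike to patients and controls. They are collection measures, however, and do not say how data that are still missing are analysed.

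Third, the full analysis set fits most naturally with an any-dose proportion, where the error can be as small as 0.5 to 2.6 points. This stands too, although 6.3.3 does not state that choice.

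A reader might infer that the trial's reactogenicity comparison is biased, or that a finding of milder reactions in patients would be an artefact. The documents do not support that: they give no return rate, nothing indicates that return differs by group, and the direction of any error is open.

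**Conclusion.** The mismatch is certain from the text: the only reactogenicity analysis uses everyone dosed, and the two populations built for it go unused. The bias is conditional. It requires that missing diaries be scored as no reaction and that return differ between groups.

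Under the assumed rates the error in the patient–control difference runs from about 0.5 to 3 points (any dose with the same reactors and independent loss, or low missingness) to about 10 points (per dose, true rate 70%, 20% against 5% missing), in either direction. The upper end needs a large difference in return that no section suggests.

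The primary endpoint is untouched, and section 6.1 describes the study as descriptive or exploratory. The missing-diary rule and the unstated dose would be ordinary gaps in detail on their own; the named denominator makes the point worth correcting. It is a minor fix.

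**What to change.** In 6.3.3, report local and systemic reactions after dose 1 and after dose 2 separately, each in its evaluable population from 6.2. Give by group and dose the number dosed, the number with any diary data and the number with a complete 7-day diary. State how unrecorded days in a partial diary are handled, because 6.2 requires only one measurement for a person to be evaluable.

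Keep the full analysis set for AE/SAE/SUSAR and for local bleeding, which does not depend on the diary (5.8.3: "Local bleeding is observed by staff after injection during the observation period"). Keep it also for an any-dose sensitivity analysis of reactions, with its missing-data rule stated. If missing is scored as no reaction, that result is a lower bound for each group's proportion, but not for the patient–control difference.

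The cost is wording and some extra counts; no new data are needed. The change must be labelled post hoc: section 2.1 already reports results from two weeks after dose 2 and from follow-up to 12 months, so the 7-day diary windows have closed. There are two downsides. The evaluable sets are unbiased only if diary return is unrelated to reacting. The dose-2 set also leaves out people whose second dose was withheld, which 5.2.4 provides for after anaphylaxis or another significant side effect likely to be related to the vaccine. The number without dose 2 and the reasons should therefore be shown by group.

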2.2. Expected results

We expect that some immunosuppressed patients will have a lower degree of immune activation and thereby potentially poorer immunity, compared with

immunocompetent individuals. Individuals who have an absence or partial deficiency in their ability to form antibodies can be expected to develop T cell immunity in certain cases. The degree of immunological response is expected to decrease over time, but it is difficult to predict the duration of a strong immunological response, as we currently lack long-term data. Reactogenicity may be milder in immunosuppressed individuals compared to immunocompetent individuals.

We expect the antibody response to decrease over time, but booster doses and/or new SARS-CoV-2 infections may increase the antibody response, while in some individuals a low/negative antibody response may continue. With the development of new variants, neutralisation capacity may change.

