4.2. Endpoints

Primary endpoint:

- Proportion (95% CI) seroconverting to a positive response to SARS-CoV-2 IgG Serology test after two doses of vaccine, measured 2 weeks after the second vaccine dose.

Secondary endpoints:

- Proportion (95% CI) seroconverting to a positive response to SARS-CoV-2 IgG serology after two doses of vaccine, at 3 months and 6 months after the second vaccine dose.
- Proportion (95% CI) experiencing adverse events, with AE/SAE/SUSAR.
- Number and proportion (95% CI) who experience local reactions and systemic reactions.
- Proportion (95% CI) who receive a new diagnosis of SARS-CoV-2 infection through a positive PCR test.

Exploratory endpoints:

- Proportion (95% CI) seroconverting to a positive response to SARS-CoV-2 IgG serology after two doses of vaccine, at 9 months, 12 months, 18 months, 24 months, 30 months, and 36 months after the second vaccine dose. This may mean that patients in routine healthcare have received one or more additional vaccine doses depending on the recommendations of the Public Health Agency of Sweden.
- A more detailed description of humoral and cellular immune responses at baseline and after vaccinations in blood and saliva at time points immediately before the first vaccine dose (day 0), day 10 after the first dose, immediately before dose 2 on day 21, and 2 weeks, 3 months, 6 months, 9 months, 12 months, 18 months, 24 months, 30 months, and 36 months after the second vaccine dose.
- Prevalence of escape mutations in SARS-CoV-2 sequencing in breakthrough infections.
- Occurrence of development/progression of graft versus host disease in allogeneic stem cell transplant recipients.
- Occurrence of biopsy-verified rejection in solid organ transplant recipients.
- Occurrence of viremia (defined as HIV RNA >50 copies/mL) after vaccination in individuals with HIV infection.
- Change in HIV DNA from study start to 3 and 6 months, 9 months, 12 months, 18 months, 24 months, 30 months, and 36 months after the second vaccine dose in individuals with HIV infection.
- Association between oral and gut microbiome and vaccine response in HIV-infected individuals and controls.

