5.3.2. Physical examinations

During the COVID-19 pandemic, physical outpatient visits for routine care at the hospital have been replaced with video visits or telephone contacts as much as possible to reduce the risk of exposure to SARS-CoV-2, especially for immunosuppressed patients who are also considered to be at higher risk of severe complications from COVID-19. This is therefore an established way of monitoring these patients in routine care. To reduce the risk of exposure to SARS-CoV-2, even when screening research subjects and during the study period, we plan to screen research subjects via video visits. During such a visit, electronic consent is planned to be obtained from the research subject and study doctor via an app, using an established and certified method, i.e. without a physical examination. However, screening via remote contact requires access to mobile Bank ID and a certain level of technical knowledge on the part of the research subject, which is why individuals (especially older individuals) who are unable or unwilling to have screening visits via remote contact in this manner will be offered a physical visit for screening. At both vaccination occasions, doctors will be on site who can perform a targeted and symptom-driven physical examination if necessary.

The rationale behind planning only targeted and symptom-driven physical examinations as needed during the study period is that we do not expect any specific side effects in the primary population related to Comirnaty, which is already an approved drug. In terms of side effects, it may rather be the opposite due to immunosuppression, with a lower frequency and severity of reactogenicity or autoimmune reactions as side effects of Comirnaty. Vaccination efficacy may prove to be suboptimal in this population, and patients therefore need to be protected from SARS-CoV-2 infection as much as possible, even in connection with measures taken in this study. The patients are well known to the clinics, where the usual follow-ups will take place within routine care during the study period. The most severely ill patients will continue to be closely monitored in routine care for their underlying disease, with physical examinations as needed in routine care.

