1.1.1.4 Assessment of systemic reactogenicity

The occurrence of fever (yes/no, if yes, temperature), fatigue, headache, chills, vomiting, diarrhea, new or worsening muscle pain, new or worsening joint pain is reported by the study subject in a diary for 7 days after dose 1 and dose 2. For individuals who have difficulty completing a diary, study staff will contact the patient on days 2 and 7 after the vaccine dose to collect data by telephone.

Table 2. Systemic Event Grading Scale

	Mild (Grade 1)	Moderate (Grade 2)	Severe (Grade 3)	Potentially Life Threatening (Grade 4)
Vomiting	1-2 times in 24 hours	>2 times in 24 hours	Requires IV hydration	Emergency room visit or hospitalization for hypotensive shock
Diarrhea	2 to 3 loose stools in 24 hours	4 to 5 loose stools in 24 hours	6 or more loose stools in 24 hours	Emergency room visit or hospitalization for severe diarrhea
Headache	Does not interfere with activity	Some interference with activity	Prevents daily routine activity	Emergency room visit or hospitalization for severe headache
Fatigue/ tiredness	Does not interfere with activity	Some interference with activity	Prevents daily routine activity	Emergency room visit or hospitalization for severe fatigue

5.8.4. eDiary

We are looking into the possibility of setting up an eDiary via Alltid öppet, where login with mobile Bank ID is required to access the diary and where study participants can register their local or systemic reactogenicity via the Alltid öppet mobile app. Study staff will have access to this data. This will be offered to study participants who are technically capable and have access to a mobile Bank ID. Alltid öppet is used in routine healthcare to send patient data, which is then entered into the patient's medical records. Similarly, we will manually record data from the eDiary in patients' medical records.

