6.4. Statistical methods

Continuous variables will be presented with mean and standard deviation [SD] for normally distributed values, and median and interquartile range (IQR) for non-normally distributed values. Categorical variables will be presented as frequency distributions.

Comparisons between patient groups and the control group will be made using the Chi-square test. P-values will be adjusted for multiple comparisons where necessary.

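### Diary severity grades are collected, but the planned reactogenicity comparison with controls uses only the proportion with a reaction; a supplementary grade-based comparison should be added

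*Combined protocol and SAP*

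**What the plan says.** The endpoint in section 4.2 is "Number and proportion (95% CI) who experience local reactions and systemic reactions". Section 6.3.3 repeats it as the analysis: "Number and proportion (95% CI) experiencing local reactions and systemic reactions are measured", with comparison against the control group. Section 6.4 supplies the test: "Comparisons between patient groups and the control group will be made using the Chi-square test". It also says that categorical variables are shown as frequency distributions and that p-values are adjusted for multiplicity where needed.

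Severity is collected. Section 5.5.3 states: "Study participants will record and rate the severity of symptoms in a diary according to 5.8.3". The local scale in 5.8.3 prints Grades 1 to 4 for injection-site pain, redness and swelling. The "Systemic Event Grading Scale" prints Grades 1 to 4 for vomiting, diarrhea, headache and fatigue. Chills, muscle pain and joint pain are diary items without a printed grade, and fever is recorded as yes/no with the temperature.

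The protocol raises severity as a question. Section 2.2 says: "Reactogenicity may be milder in immunosuppressed individuals compared to immunocompetent individuals". Section 5.3.2 considers a response "with a lower frequency and severity of reactogenicity or autoimmune reactions as side effects of Comirnaty". Section 3.2 also says that reactions may be milder in the primary population.

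**The concern.** Tolerability is a secondary objective, and the protocol's own remarks about it concern how severe reactions are as well as how often they occur. The compared quantity is a proportion with a reaction. A participant whose worst reaction falls from grade 3 to grade 1 counts the same before and after.

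The grades are not picked up elsewhere. Under 5.5.3 a diary event becomes an AE only if it meets the SAE criteria, so the investigator's severity rating in 5.8.1 does not cover ordinary reactogenicity. If reactions are about as frequent but milder in patients, the trial would report no difference although its own data show one. If both frequency and severity fall, the any/none split uses only part of the information. It uses least when nearly all controls react.

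**Working it through.** **Plan's own figure.** The only power statement (6.1: N = 540, effect size 0.15, α = 0.05, power above 80%) concerns seroconversion. Read as Cohen's w with 1 degree of freedom, the noncentrality is 540 × 0.15² = 12.15 and power is 93.6%, so the statement is met on that reading. It says nothing about reactogenicity, for which no power figure is given.

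**Inputs.** From the documents: 90 controls, 90 per patient group and 450 patients in total (5.1.1); α = 0.05 (6.1, stated for the primary endpoint); 1% severe, borrowed from the severe-pain figure in 5.8.3. Assumed, because the documents give no distribution: any reaction in 70%, 80% or 90% of controls, with 25–40% of reactors moderate.

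**Case 1: the whole distribution shifts, common odds ratio 0.5.** Patient odds of any reaction are control odds × 0.5. At 80% the odds are 0.80/0.20 = 4, then 2, so 66.7% of patients react. At 70% they are 2.333, then 1.167 (53.8%). At 90% they are 9, then 4.5 (81.8%).

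Hand check of any/none at 80% v 66.7%, 90 per group: pooled p = 0.7333; null SE = √(2 × 0.7333 × 0.2667/90) = 0.0659; alternative SE = √((0.16 + 0.2222)/90) = 0.0652. Power = Φ[(0.1333 − 1.96 × 0.0659)/0.0652] = Φ(0.06), about 53%.

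Simulated power, 20,000 trials per scenario, 90 v 90, two-sided 0.05 (gains taken before rounding):

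| Any reaction, controls | Any reaction, patients | Any/none chi-square | Wilcoxon on grade | Gain (points) |
|---|---|---|---|---|
| 70% | 53.8% | 62% | 68–70% | 6–8 |
| 80% | 66.7% | 53% | 65–69% | 13–17 |
| 90% | 81.8% | 35% | 59–66% | 24–31 |

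At a 50% control rate the gain is 2–3 points. For 450 v 90 the gains are 6–8, 13–16 and 33–39 points.

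**Case 2: severity alone shifts.** Half of the moderate or severe reactions become mild and the any-reaction rate is unchanged. At 90 v 90:

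- Any/none chi-square: about 5%, the size of the test.
- Wilcoxon: 14–25%, 21–40% and 35–62% at control rates of 70%, 80% and 90%.
- Chi-square on grade 2 or higher: 44–80% across these scenarios.

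Example: controls 10/53/36/1% (none, mild, moderate, severe) and patients 10/71.5/18/0.5%. Any reaction is 90% in both groups, while grade 2 or higher is 36 + 1 = 37% against 18 + 0.5 = 18.5%. Any/none rejects in 5.1% of trials and Wilcoxon in 61.7%.

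**Sensitivity to the assumed distribution.** With control grades 0–4 set at 20/35/30/14/1% and 6,000 trials per scenario, 90 v 90, any/none against Wilcoxon is 29% v 45% at odds ratio 0.6 and 54% v 72% at 0.5. A chi-square on all the grades gives 27% and 51%. For a severity-only shift to 20/50/23/6.5/0.5% the order changes: any/none 5–6%, Wilcoxon 37%, chi-square on all the grades 46%, grade 2 or higher 55%.

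**The case against.** The strongest reply is that the plan never restricts the comparison to any reaction versus none. Section 6.4 does not limit the chi-square to a 2×2 table, and its frequency distributions could include a table of grades. A chi-square on grades can detect a severity shift, and for a pure severity shift it does so better than Wilcoxon. This stands against two stronger readings that a reader might take: that the plan rules out any use of severity, and that an ordinal test should replace the chi-square. It does not remove the point. The quantity named in 4.2 and 6.3.3 is a proportion experiencing reactions, and no grade, threshold or ordinal test is attached to it. If grades were intended, the choice among several grade-based tests is left open in an open-label study.

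The power gain depends on how common reactions are in controls. The very common label in section 3.1 means only at least 1 in 10 per symptom, so the documents do not establish that the any-reaction rate is near its ceiling. That stands; the figures are conditional.

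Multiplicity also matters. Testing seven graded symptoms plus two overall grades, at two doses in five groups, would be 9 × 2 × 5 = 90 tests. At α = 0.05/5 = 0.01, the Wilcoxon power of 69% (80% control rate, 90 v 90) falls to 45%. Any/none falls too: Φ[(0.1333 − 2.576 × 0.0659)/0.0652] = Φ(−0.56), about 29%. The ordinal advantage remains, but the number of tests should be kept small.

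Finally, section 6.1 calls the study descriptive or exploratory, and section 2.1 shows that results at two weeks after dose 2 are already reported. An analysis added now cannot be presented as pre-specified for those data.

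**Conclusion.** The point holds as a gap between what is collected and what is compared. Ordered grades exist for seven symptoms, the protocol itself raises milder reactions, and no planned comparison uses the grade. On the plain reading of 6.3.3, a pure severity shift is missed apart from chance rejections at 5%. A general shift at odds ratio 0.5 is detected with about 35–62% power instead of 59–70% at 90 v 90. This assumes control rates of 70–90%, 25–40% of reactors moderate, 1% severe and unadjusted α = 0.05. At a control rate of 50% the difference is negligible.

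A reader might infer that a difference in severity cannot be detected at all. That is true only when the any-reaction rate is equal in the two groups and grades are ignored; otherwise the loss is one of power. Nor does the protocol predict milder reactions: its wording in 2.2 is conditional, and 5.3.2 mentions frequency as well as severity. The printed scales run from 1 to 4, with no reaction as the implied zero. In the text as read, they do not cover every systemic symptom.

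**What to change.** In 6.3.3, keep the any-reaction proportion with its 95% CI and its comparison with controls. Add, for each dose:

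- **Variable:** each participant's worst grade (none = 0) for every symptom with a printed grade, and the worst grade for local reactions and for the graded systemic symptoms overall.
- **Description:** the grade distribution, with the proportions at grade 2 or higher and grade 3 or higher (95% CI).
- **Comparison:** patient groups against controls on worst local and worst systemic grade, by Wilcoxon rank-sum test or a proportional-odds model. Use the proportion at grade 2 or higher as a supporting comparison, because it is more sensitive to a pure severity shift.
- **Limits:** per-symptom results stay descriptive, and symptoms without a printed grade stay binary. Across two overall grades, two doses and five groups this makes 2 × 2 × 5 = 20 ordinal comparisons; state how 6.4's multiplicity adjustment applies to them.
- **Label:** supplementary and, where it applies, added after the day-35 results.

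No new data are needed for the graded symptoms. The cost is a few extra tables, a less simple effect measure beside the proportion, and the additional comparisons. If the sponsor regards the addition as a change to a secondary variable, the approval route in section 8.6 applies; keeping the existing endpoint and test makes that less likely.
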